## 7.4.1.1.1 Multiplicity Adjustment for Primary Efficacy Endpoint

For the primary efficacy endpoint, if one single multivariate pMMRM model has a convergence issue after trying all the covariance structure stated above (Section 7.4.1.1), then each dose of AL002 will be compared to placebo in a pairwise manner. To adjust for multiplicity, the fixed sequence procedure (FSP) will be used (Westfall & Krishen, 2001). A fixed testing order will be used starting with the AL002 40 and 60 mg/kg combined group, followed by the highest dose, then followed by the next lower dose, and then the next lower dose. All tests will be performed at the 1-sided 0.05 level following this pre-specified order. Once one null hypothesis is not rejected, all subsequent tests will be exploratory in nature.

Protocol No. AL002-2 Last Revision Date: 12 Aug 2025

## 7.4.1.2 Supportive Analysis using Mixed-Effects Model for Repeated Measures (MMRM)

A restricted maximum likelihood based MMRM will be used as a supportive analysis to assess the primary endpoint.

The SAS® MIXED procedure will be used to fit an MMRM with CFB in CDR-SB at each scheduled post-baseline visit (Week 24, 48, 72, and 96) as the dependent variables and the fixed effects will include following items:

- Treatment group,
- Visit (categorical, as week),
- Visit-by-treatment interaction,
- Baseline CDR-SB score (covariate),
- APOE e4 status (covariate, e4 carrier vs non-e4 carrier).

An unstructured covariance matrix will be used to model within participant variance-covariance errors. If the unstructured covariance structure matrix results in a lack of convergence, the following tests will be used in sequence:

- Heterogeneous Toeplitz (TOEPH) covariance structure,
- Heterogeneous first-order autoregressive (ARH(1)) covariance structure,
- Heterogeneous compound symmetry (CSH) covariance structure,
- Toeplitz (TOEP) covariance structure,
- First-order autoregressive (AR(1)) covariance structure,
- Compound symmetry (CS) covariance structure.

In the case that a structured variance-covariance matrix is used to enable the model to converge, the "sandwich" estimator of the variance-covariance matrix will be employed by using the "empirical" option in the SAS PROC MIXED procedure.

The Kenward-Rogers approximation will be used to estimate the denominator degrees of freedom when the covariance is unstructured.

Least squares means (LSMs) and their difference between each treatment group and the placebo will be estimated for Week 24, 48, 72, 96 and "overall" (the average of Week 24, 48, 72, and 96) for each of CDR-SB. The LSMs are interpreted as the expected CFB in the primary efficacy outcome. LSMs and standard errors (SEs) will be shown for each active treatment group and placebo. In addition, the percent slowing of decline expressed as the ratio of negative difference in LSMs over the LSM of placebo (i.e., [(–difference in LSM) / (LSM of placebo)] × 100%) will be displayed for each active treatment group. And its CI will be derived using the Delta method (refer to APPENDIX for more details on the derivation).

LSMs line plots over time will be displayed for the primary endpoint with separate lines for each treatment group.

Protocol No. AL002-2 Last Revision Date: 12 Aug 2025

Additionally, the same analysis described above will be repeated with the following groups in the model: AL002 15 mg/kg group, AL002 40 and 60 mg/kg combined group, and placebo group. All statistics described above from fitting the model will be reported only for the AL002 40 and 60 mg/kg combined group (or its comparison to placebo).

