#### 7.4 Efficacy Analyses

The FAS will be used for all efficacy analyses, except for the analyses specified in Section 7.4.1.5, unless otherwise specified.

The primary estimand as described in Section 6.2.1.2 will be used for all efficacy analyses, except for the analyses specified in Section 7.4.1.5 which are based on the supportive estimand, and unless otherwise specified.

Missing data will be assumed missing at random (MAR) for all efficacy analyses, except for the analyses specified in Section 7.4.1.4, and unless otherwise specified. Sensitivity analysis to assess the impact of the missingness assumption will be performed using a Pattern Mixture Model (PMM) as described in Section 7.4.1.4.

For each continuous efficacy endpoint, the number of participants with efficacy outcomes, mean, SD, median, Q1, Q3, min, and max, at baseline and each scheduled post-baseline visit, along with CFB and PCFB to each scheduled post-baseline visit, will all be reported and accompany the estimates from the inferential statistical models. The same applies to subgroups specified in Section 7.4.3.

Unless otherwise indicated, all statistical tests will be 1-sided. However, 2-sided p-values will be reported for all tests. A significance level of 0.05 (1-sided) will be used for primary endpoint, with significance achieved if the 2-sided p-value is less than 0.10, and in the direction of indicating more efficacy for non-placebo than for placebo.

In the case of multiple values in an analysis visit window, data will be selected for analysis as described in Section 7.1.3.2, separately for each estimand.

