## 7.4.2 Analyses of Secondary Efficacy Endpoints

For the analysis of each of the secondary efficacy endpoints (Table 7-22), participants in the FAS who have a baseline value and at least one post-baseline value for the secondary endpoint being analyzed are included in the analysis.

Each of the secondary efficacy endpoints will be analyzed with pMMRM for proportional treatment effect  $(\theta)$  as described for the primary efficacy endpoint (Section 7.4.1.1). The same variables except that the baseline CDR-SB score will be replaced with the baseline for the secondary endpoint being analyzed will be included in the model.

In addition, each of the secondary efficacy endpoints will be analyzed with MMRM for CFB across all scheduled post-baseline visits and CFB to each scheduled post-baseline visit as described for the primary efficacy endpoint (Section 7.4.1.2). The same variables except that the baseline CDR-SB score will be replaced with the baseline for the secondary endpoint being analyzed will be included in the model. Also, the same analyses using the supportive estimand as described for the primary efficacy endpoint (Section 7.4.1.3) will be repeated for each of the secondary efficacy endpoints.

A forest plot of proportional treatment effect and 95% CIs from pMMRM will be drawn by treatment group for all efficacy endpoints including the primary and secondary efficacy endpoints. In the same plot, the point estimates of the proportional treatment effect will be displayed. Similarly, the forest plot of LSM difference at Week 96 and 95% CIs from MMRM will be drawn by treatment group for all efficacy endpoints. In the same plot, the point estimates of the LSM difference at Week 96 and the percent slowing of decline will be displayed side by side. The same forest plot for the LSM difference at "overall" from MMRM will be provided.

a same method as in Section 7.4.1.1

b same model as in Section 7.4.1.2

Protocol No. AL002-2 Last Revision Date: 12 Aug 2025

All secondary efficacy endpoints will be analyzed without adjustment for multiplicity and presented with nominal p-values.

Table 7-22. Analyses of Secondary Efficacy Endpoints

Secondary Endpoints	Methodology a
CFB in MMSE to Week 24, 48, 72, 96	pMMRM b , MMRM c
CFB in RBANS to Week 24, 48, 72, 96	pMMRM b , MMRM c
CFB in ADAS-Cog13 to Week 24, 48, 72, 96	pMMRM b , MMRM c

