#### 9. CHANGES FROM METHODS PLANNED IN THE PROTOCOL

The statement of the primary estimand given in Section 6.2.1.2 clarified that the target population excludes e4/e4 participants, that the primary estimand specified in the latest version of the protocol did not specify this exclusion. This clarification does not result in any differences for summaries or analyses.

The criteria for PPS in Section 5.3.2 are updated as the one specified in the protocol was too general and did not meet the needs of PPS.

The summary of physical examinations will not be performed, since clinically significant physical examination changes will be captured in the AE summaries.

The supportive analysis using LME model is removed from this SAP. The primary analysis using the pMMRM model is based on the assumption of proportionality, which is an inherit assumption of the LME model. If the assumption of proportionality is not met under the pMMRM model, the results of analysis using the MMRM model will be used to interpret the study. For this reason, the supportive analysis using LME model has been removed from SAP.

Safety analyses will primarily be performed for the Non-e4/e4 Set, instead of the Safety Set as specified in the protocol, because of the removal of the e4/e4 participants from the participant population being studied. The AL002-2 study originally included enrollment of participants who were APOE e4 homozygotes (e4/e4). However, further enrollment of participants with this APOE genotype was permanently stopped after the evaluation of safety among the early enrolled participants with e4/e4. Therefore, the primary objective of the study changed to the assessment of AL002 in the participants without e4/e4.

The exploratory analyses of WLSA data (optional study) and genetics will be excluded from the SAP.

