#### 12. APPENDIX

#### Delta method:

Let X and Y be two random variables with means  $\mu_X$  and  $\mu_Y$ , respectively; and let  $R(\mu_X, \mu_Y) = \frac{\mu_X}{\mu_Y}$  be the ratio. Then

$$\frac{\partial y}{\partial \mu_X} R (\mu_X, \mu_Y) = \frac{1}{\mu_Y}$$

$$\frac{\partial y}{\partial \mu_Y} R (\mu_X, \mu_Y) = -\frac{\mu_X}{\mu_Y^2}$$

$$E\left(\frac{X}{Y}\right) \approx \frac{\mu_X}{\mu_Y} \qquad (1)$$

$$Var\left(\frac{X}{Y}\right) \approx \frac{1}{\mu_Y^2} VarX + \frac{\mu_X^2}{\mu_Y^4} VarY - 2\frac{\mu_X}{\mu_Y^3} Cov(X, Y)$$

When *X* and *Y* are independent (e.g., in two independent treatment arms),

$$Var\left(\frac{X}{Y}\right) \approx \frac{1}{\mu_Y^2} VarX + \frac{\mu_X^2}{\mu_Y^4} VarY$$
 (2)

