#### Percent slowing of decline estimation based on MMRM

When applying the Delta method to the MMRM outputs,  $\mu_X$  and  $\mu_Y$  will be substituted by the estimated LSMs of the CFB at the end-of-study visit (time = 4 in the specific example below), and their variances will be the estimated variances. The table below presents the related parameter estimates that can be used for the percent slowing of decline estimation. Substituting these related estimates into formula (1) and formula (2) will yield the percent slowing of decline estimation and the corresponding p-values.

Group	Time	Estimate	Standard Error
P	4	$\mu_Y = 4.5489$	$\sqrt{VarY} = 0.6143$
T	4	$\mu_X = 3.0991$	$\sqrt{VarX} = 0.5903$

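### The Delta-method interval and p-value for MMRM percent slowing lean toward benefit and can disagree with the LSM-difference test from the same output

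*SAP*

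**What the plan says.** SAP 7.4.1.2 estimates LSMs and their differences from placebo at Weeks 24, 48, 72 and 96 and overall. It then adds, for each active group, "the percent slowing of decline expressed as the ratio of negative difference in LSMs over the LSM of placebo", and states: "And its CI will be derived using the Delta method". That sentence names neither a visit nor a confidence level.

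Appendix 12 supplies the formulas. Formula (1) is the ratio of the treatment LSM (X) to the placebo LSM (Y). Formula (2) is its Delta-method variance without the covariance term, for the case where the two "are independent (e.g., in two independent treatment arms"). The appendix works at the end-of-study visit and adds: "Substituting these related estimates into formula (1) and formula (2) will yield the percent slowing of decline estimation and the corresponding p-values". It gives a table of illustrative inputs but prints no resulting interval or p-value.

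Three other places matter:
- Section 7.4 sets the primary endpoint at one-sided 0.05, "with significance achieved if the 2-sided p-value is less than 0.10".
- Section 7.4.2 says "the forest plot of LSM difference at Week 96 and 95% CIs from MMRM will be drawn", with percent slowing shown alongside as a point estimate.
- Section 9 says that if proportionality is not met, "the results of analysis using the MMRM model will be used to interpret the study".

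Nothing says which result prevails if the percent-slowing interval or p-value disagrees with the LSM-difference test.

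**The concern.** Zero percent slowing and zero LSM difference are the same hypothesis, so one model should not give two answers to it. The Delta method can. The estimated placebo decline sits in the denominator, so a placebo estimate that is high by chance raises the estimated slowing and shrinks its Delta standard error at the same time. The lower limit then lies above the truth too often, and the upper limit almost never falls below it. The error favours AL002.

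Percent reduction relative to placebo is also the scale of the primary estimand. If the MMRM had to carry the interpretation under Section 9, percent slowing would be a natural figure to quote.

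**Working it through.** **Inputs (SAP Appendix 12 table).** Placebo Y = 4.5489, SE 0.6143. Treatment X = 3.0991, SE 0.5903. Covariance 0, as in formula (2). Normal quantiles are used. The SAP prints no result for this example, so there is no figure to reproduce.

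**Delta method.**
- Slowing = 1 - X/Y = 1 - 3.0991/4.5489 = 1 - 0.6813 = 31.9%. Subtracting from 1 leaves the variance unchanged.
- Var(X/Y) = VarX/Y² + X²VarY/Y⁴ = 0.01684 + 0.00846 = 0.02530, so SE = 0.1591.
- z = 0.3187/0.1591 = 2.004, two-sided p = 0.045.
- 95% CI: 31.9% ± 1.96 × 15.9 points = 0.7% to 63.0%. 90% CI: 5.7% to 58.0%.

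**LSM difference.**
- 4.5489 - 3.0991 = 1.4498; SE = √(0.6143² + 0.5903²) = 0.852.
- z = 1.702, two-sided p = 0.089; 95% CI -0.22 to 3.12.

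**Why they differ.** Multiplying the numerator and denominator of the Delta z by Y gives z = (Y - X)/√(VarX + R²VarY), with R = X/Y. The difference test uses VarX + VarY. With independent LSMs and a positive placebo LSM, any estimate in favour of treatment (R between 0 and 1) has its placebo variance multiplied by a factor below 1. Here R² = 0.464, so the denominator is √(0.3485 + 0.464 × 0.3774) = 0.724, and 1.4498/0.724 = 2.00.

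**Fieller interval.** The limits for R solve (Y² - z²VarY)R² - 2XYR + (X² - z²VarX) = 0.
- 95%: 19.243R² - 28.195R + 8.266 = 0 gives R = 0.405 and 1.060, so slowing is -6.0% to 59.5%.
- 90%: slowing is 1.3% to 55.4%.
- Putting R = 1 into the left side gives (Y - X)² - z²(VarX + VarY). When the interval is bounded, it therefore excludes zero slowing exactly when the difference test rejects.

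**One-sided error.** Simulation with 2,000,000 draws, zero true slowing (both means 4.5489), the appendix SEs and independent normal LSMs:

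| Level | Delta lower limit above 0 | Nominal | Difference test | Delta upper limit below 0 | Delta two-sided coverage |
|---|---|---|---|---|---|
| 95% | 4.4% | 2.5% | 2.5% | 0.3% | 95.3% |
| 90% | 7.3% | 5% | 5.0% | 1.7% | 91.0% |

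**Dependence on the placebo coefficient of variation (CV).** In the appendix this is 0.6143/4.5489 = 0.135. If the CV were 0.25, 0.35 or 0.5, the 95% lower limit would exceed zero in about 5.7%, 6.5% or 7.2% of trials. These CVs are assumptions for early visits or small subgroups, where placebo decline is small or imprecise. The rates move by a few tenths of a point with the ratio of the two SEs.

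**The case against.** A reader might infer that the SAP's own example contradicts itself at the trial's decision level. It does not. The primary rule is a two-sided p below 0.10, which 0.089 meets, and at 90% both intervals exclude zero. The 95% level is a reading: Section 7.4.1.2 gives none for percent slowing, though Section 7.4.2 uses 95% for the MMRM differences. Even at 95% the exclusion of zero is narrow. With t quantiles it holds from about 58 degrees of freedom and is lost at 50 (lower limit -0.1%). With an LSM correlation of 0.3 both methods exclude zero; from 0.05 to 0.2 the disagreement remains. The numbers are illustrative, not trial data.

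A reader might also call the interval too short. Two-sided coverage is 95.3%, so it is shifted rather than short. Nor does the SAP clearly promise this interval at Week 24: the percent-slowing sentence names no visit, and the appendix uses the end-of-study visit.

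Finally, the analysis is supportive. The primary estimate comes from the pMMRM with its own intervals. Section 9 refers to MMRM results in general, which include the unaffected LSM difference, and does not tie interpretation to the percent-slowing interval.

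All of this stands and limits the reach of the point. It does not remove the one-sided excess, which is present at 90% as well as 95% and does not depend on a borderline example. It also leaves in place the plan to issue a second p-value for the same hypothesis.

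**Conclusion.** The point holds as a fault in a supportive output. The planned interval and p-value for MMRM percent slowing favour AL002. At the appendix SEs the benefit-side error is 4.4% against a nominal 2.5% at the 95% level, and 7.3% against 5% at the 90% level. The appendix inputs give p = 0.045 for percent slowing beside p = 0.089 for the LSM difference.

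These rates assume independent normal LSMs with the appendix's SEs. Higher rates rest on assumed larger placebo CVs. The documents do not support reading this as a threat to the primary pMMRM test or to the MMRM LSM difference, nor as a contradiction at the trial's one-sided 5% level in the example. The change is worth making because the error has a known direction and a cheap remedy.

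**What to change.** In SAP 7.4.1.2 and Appendix 12:

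- Take the p-value for percent slowing from the MMRM LSM-difference test. This alone removes the conflicting p-values.
- Replace the Delta interval with a Fieller interval built from the placebo LSM, the LSM difference and their covariance from PROC MIXED. Use the same confidence level as for the LSM difference, and state that level and the visits covered.
- Where the placebo LSM is not distinguishable from zero, report the Fieller set as unbounded and rely on the LSM difference. Do not drop the interval: reporting only when placebo decline looks large brings back part of the bias. In simulation with zero true slowing, dropping such intervals removes about 18% of them at a placebo CV of 0.35 and 48% at 0.5, and 3.1% and 4.8% of those still reported lie wholly above zero (nominal 2.5%).
- Apply the same rule wherever the MMRM percent slowing is given with an interval, including the combined 40 and 60 mg/kg group, secondary endpoints and subgroups.

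The cost is SAP wording and a few lines of code on existing output, with no new data. Some intervals will become wider, asymmetric or unbounded. A log-scale Delta interval also includes zero at 95% in the example (-7.7% to 56.9%), but Fieller is preferable because it agrees with the difference test by construction.

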#### 7.4.1.3 Analyses of Supportive Estimand for Primary Efficacy Endpoint

The analyses described in Sections 7.4.1.1 (pMMRM), and 7.4.1.2 (MMRM) will be repeated with the supportive estimand for the primary efficacy endpoint, as described in Section 6.2.1.3.

#### 7.4.1.4 Sensitivity Analysis using Control-Based Pattern Mixture Model

To evaluate the impact of different patterns of missing CDR-SB values, a PMM with the primary estimand for the primary efficacy endpoint will be used in this study as a sensitivity analysis. PMMs have the advantages of allowing transparent and clinically interpretable formulations of the assumptions regarding unobserved data (Little & Rubin, 2019).

After the intermittent missing data are imputed, impute monotone missing at visits, up to the treatment period termination date (as defined in the protocol) plus 37 days, using a control-based PMM under the MNAR assumption. This is done because monotone missing data are presumed to be no longer on study drug, so could be treated as placebo control. Missing data will be imputed using sequential regression control-based pattern MI, where a separate regression model is estimated for imputation of each measurement at each visit.

The following sequential regression control-based pattern MI steps will be used:

- i. With each call to PROC MI, only one time-point will be imputed. Each regression model will include explanatory variables: post-baseline measurement, APOE e4 status (e4 carrier, non-e4 carrier), all previous measurements at each time point (up to the missing value time-point). Range restrictions implied to imputed CDR-SB score: 0-18. Imputed data will consist of 100 imputed datasets.
- ii. When imputing missing values for time-point *t*, the input dataset should include all placebo participants, but only those participants from AL002 that have values at time-point *t* missing (only those that need imputation at time-point *t*). Since participants from AL002 treatment groups with non-missing values at time-point *t* will not be included in the input dataset, they will not contribute to the estimation of an imputation model for time-point *t*. Imputation model will be estimated using placebo participants only. This way, missing values of participants from AL002 will be imputed based on the placebo participants' model.
- iii. Repeat step ii for all other time-points sequentially. Participants whose missing values were imputed with the previous PROC MI call will be included in the input dataset for the next call to PROC MI. Thus, data for time-point t, filled in during the last call, will be used for predictor variables in the next call to PROC MI (for time-point t + 1).
- iv. The multiple-imputed datasets of CDR-SB values will be used to compute the CFB in CDR-SB.
- v. Perform the same primary analysis (pMMRM) with CFB in imputed or observed CDR-SB values and combine the results (mean differences and standard errors from multiple pMMRM) based on a standard MI methodology (Rubin 1987).

Protocol No. AL002-2 Last Revision Date: 12 Aug 2025

100 independent replications will be done with SAS PROC MI. The resulting 100 estimates of the treatment differences and standard errors will then be combined into the final estimate using SAS PROC MIANALYZE. Sample SAS codes for the MIs will be provided in a separate document. If changing seeds does not provide sufficient accuracy (two decimal places) for estimated standard errors, a larger number of replications will be used (i.e., start with 100, then maybe 200 or 500).

The control-based PMM analysis described above will be repeated with MMRM (Section 7.4.1.2), i.e., the pMMRM analysis will be replaced with MMRM in the step v.

### 7.4.1.5 Supplementary Analyses on Per-Protocol Analysis Set (PPS)

Supplementary analyses on PPS will be performed as follows (Table 7-21):

Table 7-21. Supplementary Analyses on PPS

Primary Efficacy Endpoint	Timing	Methodology
CFB to all scheduled post-	Week 24, 48, 72, 96	pMMRM a
baseline visits in CDR-SB score		MMRM b

pMMRM = proportional Mixed-Effects Model for Repeated Measures, MMRM = Mixed-Effects Model for Repeated Measures.

## 7.4.2 Analyses of Secondary Efficacy Endpoints

For the analysis of each of the secondary efficacy endpoints (Table 7-22), participants in the FAS who have a baseline value and at least one post-baseline value for the secondary endpoint being analyzed are included in the analysis.

Each of the secondary efficacy endpoints will be analyzed with pMMRM for proportional treatment effect  $(\theta)$  as described for the primary efficacy endpoint (Section 7.4.1.1). The same variables except that the baseline CDR-SB score will be replaced with the baseline for the secondary endpoint being analyzed will be included in the model.

In addition, each of the secondary efficacy endpoints will be analyzed with MMRM for CFB across all scheduled post-baseline visits and CFB to each scheduled post-baseline visit as described for the primary efficacy endpoint (Section 7.4.1.2). The same variables except that the baseline CDR-SB score will be replaced with the baseline for the secondary endpoint being analyzed will be included in the model. Also, the same analyses using the supportive estimand as described for the primary efficacy endpoint (Section 7.4.1.3) will be repeated for each of the secondary efficacy endpoints.

A forest plot of proportional treatment effect and 95% CIs from pMMRM will be drawn by treatment group for all efficacy endpoints including the primary and secondary efficacy endpoints. In the same plot, the point estimates of the proportional treatment effect will be displayed. Similarly, the forest plot of LSM difference at Week 96 and 95% CIs from MMRM will be drawn by treatment group for all efficacy endpoints. In the same plot, the point estimates of the LSM difference at Week 96 and the percent slowing of decline will be displayed side by side. The same forest plot for the LSM difference at "overall" from MMRM will be provided.

a same method as in Section 7.4.1.1

b same model as in Section 7.4.1.2

Protocol No. AL002-2 Last Revision Date: 12 Aug 2025

All secondary efficacy endpoints will be analyzed without adjustment for multiplicity and presented with nominal p-values.

Table 7-22. Analyses of Secondary Efficacy Endpoints

Secondary Endpoints	Methodology a
CFB in MMSE to Week 24, 48, 72, 96	pMMRM b , MMRM c
CFB in RBANS to Week 24, 48, 72, 96	pMMRM b , MMRM c
CFB in ADAS-Cog13 to Week 24, 48, 72, 96	pMMRM b , MMRM c
CFB in ADCS-ADL-MCI to Week 24, 48, 72, 96	pMMRM b , MMRM c
CFB in ADCOMS to Week 24, 48, 72, 96	pMMRM b , MMRM c
CFB in modified iADRS to Week 24, 48, 72, 96	pMMRM b , MMRM c

pMMRM = proportional Mixed-Effects Model for Repeated Measures, MMRM = Mixed-Effects Model for Repeated Measures.

